### **3.b Treatment Regimen**

Tofacitinib will be taken as extended release, 11mg, once daily.

### **3.c Method for Assigning Subjects to Treatment Groups**

All subjects will be in the same treatment group.

### **3.d Preparation and Administration of Study Drug**

Preparation is not required. Study Drug will be provided by Pfizer, the manufacturer of the drug. The research team will provide pre-packaged bottles to the patients. Patients will self-administer the study drug.

### **3.e Subject Compliance Monitoring**

Patients will be asked about medication adherence during regular clinical follow-up.

### **3.f Prior and Concomitant Therapy**

All patients will be prescribed steroids with a uniform and pre-determined taper starting at prednisone 60mg daily (or equivalent) and tapering over 14 weeks to off.

Patients intolerant to an initial steroid-sparing therapy (e.g. methotrexate, azathioprine, or mycophenolate) will be started on tofacitinib and their prior steroid-sparing therapy will be discontinued. No other steroid sparing therapy will be initiated during the study period to avoid confounding of clinical efficacy.

Patients tolerant to prior steroid sparing therapy but with an incomplete control of their disease will have tofacitinib added to their steroid-sparing therapy. No other steroid sparing therapy will be initiated during the study period to avoid confounding of clinical efficacy.

Concomitant therapy with biologic steroid-sparing therapy such as adalimumab is prohibited due to the risk of infection.

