## **E Study Design**

### **E1 Overview or Design Summary**

This study is a prospective, single-site, open-label investigation of tofacitinib for refractory uveitis. The study will be for 24 weeks, with potential 1-year extension for treatment responders. The patients will self-administer the medication.

Eligible patients would be those patients with a diagnosis of uveitis who meet the following criteria:

- 1) Disease sufficiently severe to require treatment with systemic corticosteroids, and
- 2) Referred from Ophthalmology to Rheumatology or Uveitis specialist for a steroid-sparing agent

For patients naive to oral steroid-sparing therapy (e.g., methotrexate, azathioprine, or mycophenolate), tofacitinib will be initiated as monotherapy. For patients who have failed or had only a partial response to oral steroid-sparing therapy, tofacitinib will be initiated as an add-on therapy. For patients intolerant to a conventional agent, tofacitinib will be initiated as replacement monotherapy. For patients who have failed biologic therapy (e.g. adalimumab), biologic therapy will be discontinued and tofacitinib will be initiated as replacement therapy without change to concurrent conventional steroid-sparing agents. Study visits will occur at baseline/enrollment, and weeks 4, 8, 12, 16, & 24 (+/- 2 weeks). Clinic visits may occur more frequently as determined by the treating physician. Laboratory monitoring (Table 1) will be obtained according to standard of care for drug toxicity monitoring. Clinical responses will be evaluated at 24 weeks, with the primary outcome defined as treatment failure.

All patients will undergo a predetermined oral steroid taper starting at 60mg of prednisone (or equivalent) and tapering over 14 weeks (Table 2). All patients will undergo a predetermined topical steroid drop taper starting at their current dose (Table 3).

Patients will have an ophthalmological evaluation by their treating ophthalmologist at Washington University. Steroid sparing therapy will be managed by rheumatologists or uveitis specialists at Washington University. All patients will be evaluated for an associated systemic rheumatologic condition.

---

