## **E2 Subject Selection and Withdrawal**

### **2.a Inclusion Criteria**

- 18 years of age or older
- diagnosis of uveitis
- for patients with uveitis (documented in medical record):
  - prior treatment failure with adalimumab
  - medical contraindication to adalimumab
  - patient unable or unwilling to perform self-injections
  - patient unable to obtain adalimumab due to cost or insurance
- a clinical response to steroids
- active disease requiring at least 10mg of prednisone (or steroid equivalent) for 2 or more weeks
  - active disease is defined as any of the following
    - at least one active inflammatory chorioretinal or retinal vascular lesion
    - anterior chamber cell grade of 2+ or higher (according to Standardization of Uveitis Nomenclature Working Group criteria)
    - vitreous haze grade of 2+ or higher (according to National Eye Institute [NEI] criteria adapted by the Standardization of Uveitis Nomenclature Working Group)
- practice of preventative contraception for women of childbearing age

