### **2.b Ethical Considerations**

There is one FDA-approved steroid-sparing therapy for uveitis (adalimumab). Tofacitinib and adalimumab are equally effective in treating the associated systemic disorder, psoriatic arthritis. For patients who have failed adalimumab, tofacitinib offers a reasonable alternative therapy.

Patients will have regular follow-up with both Ophthalmology and Rheumatology to monitor disease activity. Treatment with corticosteroids will be available for rescue therapy for all patients with uncontrolled disease.

Patients may be influenced to participate because an authority figure (their physician) may propose the study, however, steps that will be taken by the research team to minimize the possibility of coercion or undue influence during the consent process. The consent process will include full study disclosure, giving the patient a reasonable amount

---

of time to decide regarding participation and the opportunity to discuss with family and friends, and assuring the patient that they will receive the same quality of care regardless of study participation.

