## **2.e Risks and Benefits**

As with other immunosuppressive treatments to control autoimmune diseases, the patients will be at increased risk of infection (20%). Other risks include nasopharyngitis (3% to 14%), hypertension (2%), headache (4% to 9%), rash (6%), acne vulgaris ( $\geq 2\%$ ), increased serum cholesterol (5% to 9%), diarrhea (4% to 5%), gastroenteritis (4%), nausea (4%), urinary tract infection (2%), anemia (4%), herpes zoster infection (5%; including disseminated cutaneous, meningoencephalitis, ophthalmologic), increased creatine phosphokinase (3% to 7%), increased serum creatinine ( $< 2\%$ ), upper respiratory tract infection (4% to 6%), and fever ( $\geq 2\%$ ).

Lymphoma and other malignancies have been reported in patients receiving tofacitinib

Tuberculosis (pulmonary or extrapulmonary) has been reported in patients receiving tofacitinib. Standard laboratory screening is performed in all patients to assess for latent / chronic infection, such as TB.

There is a risk associated with lack of efficacy. In the case of a treatment failure based on the primary outcome criteria, tofacitinib will be discontinued and the patient will be switched to an alternative steroid-sparing therapy at the discretion of the patient's treating physician.

Potential benefits include improved control of the ocular inflammatory disease, reduced corticosteroid usage, reduced intraocular pressure, improved visual acuity, and prevention of permanent vision loss. The participants may also derive benefit from contributing to medical research.

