### ***F4 Subsequent visits (weeks 4, 8, 12, 16, 24 or Early Exit Visit)***

- Concomitant Medication collection
  - Dose of medications used to treat increased intraocular pressure
  - Dose of topical and/or systemic corticosteroids
- Ophthalmology data
  - Anterior chamber cell
  - Vitreous haze
  - Retinal lesions
  - Visual Acuity

- 
- Cystoid macular edema
  - Intraocular pressure
  - Adverse event collection
  - Collection of used drug bottle and dispense of new drug bottle for use (drug accountability)

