## **H Data Handling and Record Keeping**

### ***H1 Confidentiality and Security***

Consents will be scanned into the medical record. Original hard copies of consents will be secured under two keys and two locks in a locked file-cabinet within a locked office. Prospective clinical data will be collected during the study and entered into RedCap (a HIPAA compliant and password-protected database.) All aspects of the medical record will be analyzed including age, sex, office visit data, phone number, MRN, chief complaint, history of present illness, past medical and surgical history, past ocular history, medications, allergies, exam findings, studies including images, ultrasound, and radiographic studies, laboratory data, diagnosis, assessment and plan as well as clinical outcomes.

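### In add-on patients who have not failed a biologic, section 3.f bars starting another steroid-sparing agent but not raising the dose of the one they keep

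*Combined protocol and SAP*

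**What the plan says.** Section E1 sorts patients by treatment history. Those naive to oral steroid-sparing drugs start tofacitinib alone, and those intolerant of a conventional agent have it replaced. The group at issue is described so: "For patients who have failed or had only a partial response to oral steroid-sparing therapy, tofacitinib will be initiated as an add-on therapy". For patients who have failed a biologic, E1 stops the biologic and starts tofacitinib "without change to concurrent conventional steroid-sparing agents".

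Section 3.f repeats the add-on arrangement for patients who tolerate their agent but are not fully controlled. It then sets the limit and gives the reason: "No other steroid sparing therapy will be initiated during the study period to avoid confounding of clinical efficacy".

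Patients can reach the add-on group without a failed biologic. The inclusion criteria (E2, 2.a) list four adalimumab-related conditions, one of which is "patient unable or unwilling to perform self-injections".

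F3 and F4 collect concomitant medication at each visit. The doses they name are those of pressure-lowering drugs and, in the plan's words, "Dose of topical and/or systemic corticosteroids". H1 adds that "All aspects of the medical record will be analyzed", and its list includes medications.

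**The concern.** The stated purpose of the limit in 3.f is wider than the limit itself. It guards against a second steroid-sparing drug being started, but a larger dose of the drug already on board could confound the result in the same way.

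The trial has one arm, and G3 sets its failure rate beside an external placebo failure rate of 80%. Suppose an add-on patient flares mildly as prednisone comes down, the methotrexate, azathioprine or mycophenolate dose is raised, and the eye settles. That patient counts as a non-failure on tofacitinib, although the background drug may have done part of the work. What is at stake is how individual outcomes are read, in a study small enough that each one matters.

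**Working it through.** The plan gives no figure for this point, so there is none to reproduce. The check is mainly a comparison of texts.

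**1. Which patients are exposed (E1 and 3.f).**
- Naive to oral agents: no background agent, so not exposed.
- Intolerant: the agent is stopped, so not exposed.
- Failed a biologic: conventional agents are left unchanged under E1, so covered.
- Failed or partly responded to an oral agent, with no biologic failure: the agent is kept and no dose rule is stated, so exposed.

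**2. Can the exposed group enrol?** I read the four adalimumab conditions in 2.a as alternatives, which is an assumption about the list. Three of the four need no biologic failure: a medical contraindication, inability or unwillingness to self-inject, and cost or insurance. So the group can enter.

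**3. Does any other section close the gap?**
- 2.a asks for no stable background dose before entry.
- 2.j deals only with reducing tofacitinib.
- Tables 2 and 3 fix only the oral and topical corticosteroid tapers.
- E1 places steroid-sparing therapy under the treating rheumatologists or uveitis specialists and sets no dose limit for the add-on group.

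None of these restricts a background dose increase.

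**4. Could such a patient still be scored a non-failure?** After week 8, C1 needs a 2-step rise in anterior chamber cell or vitreous haze, a new lesion, or a loss of two or more rows of acuity. A 1-step rise alone is not failure. Table 2 takes prednisone from 10 mg at week 8 to 0 at week 15, so inflammation may well return in this period. An increase in the background drug for a 1-step rise therefore breaks no stated rule, and the patient can finish as a non-failure.

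**5. Weight of one patient.** G1 sets a maximum of 5 patients. 1/5 = 20 percentage points, and more if fewer enrol.

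**6. How many outcomes could be affected.** The documents do not say how many patients will be add-on, so the range is 0 to 5. Only non-failures can be credited wrongly to tofacitinib. Taking G3's expected 40-60% as failures gives 0.40 x 5 = 2 to 0.60 x 5 = 3 failures, leaving 5 - 3 = 2 to 5 - 2 = 3 non-failures. On that expectation, 0 to 3 outcomes could be affected. This is a ceiling, not a forecast.

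**The case against.** The strongest reply is that this is a drafting gap with an inferable intent. The purpose clause in 3.f points to stable background therapy. 2.b names a different outlet for a flare: "Treatment with corticosteroids will be available for rescue therapy for all patients with uncontrolled disease". 2.e puts a change of agent after failure, when "the patient will be switched to an alternative steroid-sparing therapy at the discretion of the patient's treating physician". A reader might infer that the plan intends or invites escalation of the background drug. The documents do not support that; they only fail to forbid it.

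A reader might also infer that an increase would go unseen. That does not follow either. Concomitant medication is collected at every visit, H1 brings medications into the analysis, and I1 has the investigators meet weekly to review study data, including drug exposure. At one site with at most 5 patients, an increase would probably be noticed. This part of the reply stands, and it limits the harm. Two gaps remain: the background agent's dose is not a named item, and no section asks for a change to be shown beside the outcome. Seeing a change afterwards also does not separate the two drugs' effects.

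The third reply is that fixing the dose leaves other confounding in place. Every add-on patient receives two drugs and a prednisone taper, and corticosteroid rescue is not a failure criterion in C1. This is right. A stable dose does not isolate tofacitinib. It does keep the background drug at the dose that had already proved insufficient, which makes the outcome easier to read. The rescue point is met by flagging rescue in the results as well.

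**Conclusion.** The point holds as a minor one. For add-on patients who have not failed a biologic, the rule in 3.f is narrower than its stated aim, and E1's no-change wording does not reach them. A dose increase for inflammation short of C1 failure would break no stated rule and could end as a non-failure credited to tofacitinib.

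Each patient is worth at least 20 percentage points, but the number affected is unknown and may be zero. G1, G3 and G4 make the analysis descriptive, so no test or error rate is touched.

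A reader might infer that the gap would move the observed failure rate by a known amount, or remove the contrast with the external 80%. The documents do not support that. Nothing in the plan reclassifies such a patient, nothing says how often an increase would occur, and any single patient among 5 carries the same weight whatever the cause. Nor should all 24 weeks be treated as equally exposed: an increase shortly before week 24 has little time to act, and the period of interest ends at treatment failure.

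The conclusion assumes that the four adalimumab conditions are alternatives, that initiating a therapy does not include raising the dose of a current one, and that a higher background dose could reduce inflammation within the study period.

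**What to change.** In 3.f, extend E1's principle to all retained agents:

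> Any conventional steroid-sparing agent retained at entry is continued without dose increase from week 0 to week 24 or treatment failure; reductions for toxicity are allowed.

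Add the retained agent's dose as a named entry under the existing concomitant-medication item in F3 and F4. In the per-patient descriptive results, show whether each patient was on monotherapy or add-on therapy, and flag any background dose increase or corticosteroid rescue before week 24. Leave the C1 failure definition unchanged: C3 bases the outcome measures on published phase 3 trials, and G3 sets the result beside an external rate. Patients with an increase need not be recounted as failures.

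The cost is one sentence, one dose entry per retained agent per visit, and the flags in the results. For one agent per patient that is at most 1 x 6 visits x 5 patients = 30 entries. No visit or procedure is added. The downside is slightly less freedom to adjust the background drug for inflammation short of failure; corticosteroid rescue under 2.b remains available.

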### **3.g Packaging**

Packaging will be provided by Pfizer, the manufacturer of the drug.

### **3.h Blinding of Study Drug**

There is no blinding.

### **3.i Receiving, Storage, Dispensing and Return**

The study drug will be shipped to the PI who will store the drug in a locked room at room temperature. An established and validated local temperature management system with temperature logs will be used to record the storage temperature. The research team will dispense the drug to the patients during their clinical visit.

---

## **F Study Procedures**

---

### ***F1 Screening for Eligibility***

Clinicians on the research team will identify potential participants via a computerized search for relevant diagnoses and via clinical identification of uveitis during patient encounters. The clinician and/or research coordinator will discuss the study with potential participants either during the patient encounter. Consent will be signed prior to drug administration.

### ***F2 Schedule of Measurements***

Patients will have scheduled visits with a research clinician on weeks 0 (baseline), 4, 8, 12, 16, & 24 (+/- 2 weeks) as described in Table 1. These visits are standard of care for the treatment of uveitis. Measurements taken during these visits are part of standard of care.

Laboratory measurements for steroid-sparing therapy will be obtained according to Table 1.

### ***F3 Initial Visit (week 0; baseline)***

- Informed consent
- Inclusion/Exclusion criteria verification
- Medical history and Demographics
- Concomitant Medication collection
  - Dose of medications used to treat increased intraocular pressure
  - Dose of topical and/or systemic corticosteroids
- Ophthalmology data
  - Anterior chamber cell
  - Vitreous haze
  - Retinal lesions
  - Visual Acuity
  - Cystoid macular edema
  - Intraocular pressure
- Provide Subject Study Handout
- Provide Drug Package Insert
- Dispense Study Drug

### ***F4 Subsequent visits (weeks 4, 8, 12, 16, 24 or Early Exit Visit)***

- Concomitant Medication collection
  - Dose of medications used to treat increased intraocular pressure
  - Dose of topical and/or systemic corticosteroids
- Ophthalmology data
  - Anterior chamber cell
  - Vitreous haze
  - Retinal lesions
  - Visual Acuity

- 
- Cystoid macular edema
  - Intraocular pressure
  - Adverse event collection
  - Collection of used drug bottle and dispense of new drug bottle for use (drug accountability)

## **F5 Safety and Adverse Events**

### **5.a Safety and Compliance Monitoring**

Safety and compliance monitoring will be performed at each visit by research clinician in Rheumatology, e.g. Drs. [name], [name], [name], & [name] or [name] in Ophthalmology.

Patients will return empty bottles of tofacitinib to demonstrate compliance.

### **5.b Medical Monitoring**

#### **i Investigator only**

The principle investigator will review the study data every 6 months until study completion.

### **5.c Definitions of Adverse Events**

Any unfavorable medical occurrence in a human subject including any abnormal sign, symptom, or disease.

Some possible adverse event include:

1. Drug Reaction
  - This includes a rash, drug hypersensitivity or allergic reaction.
2. Laboratory abnormality
  - Elevation of ALT, AST, or creatinine on complete metabolic panel above baseline and three times above the upper limit of normal
  - Decrease of white blood cell count, absolute neutrophil count, hemoglobin, platelet count below baseline and below the normal range
  - Increase of blood lipid and cholesterol levels above baseline and above the normal range
3. Infection
  - This includes bronchitis, influenza, nasopharyngitis, pharyngitis, rash, upper respiratory tract infection, and urinary tract infection.
4. Malignancy
  - Any new diagnosis of malignancy during the study period will be recorded.
5. Hospitalization
  - Any hospitalizations during the study period and the primary diagnosis for hospitalization will be recorded.

---

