## **2.i Cessation of tofacitinib therapy**

### **i Indications for cessation of tofacitinib therapy**

- Laboratory abnormalities:
  - New elevation of ALT or AST > 3x upper limit of normal
  - New leukopenia with ANC < 1.5
  - New anemia with hemoglobin <7 g/dl or a decrease of > 3g/dl
  - New renal failure that would preclude the safe administration of tofacitinib
    - Patients may restart tofacitinib after recovery of renal function
- Clinical events:
  - Shingles or opportunistic infection:
    - Patients that develop an opportunistic infection or shingles may opt to (1) withdraw from the study or (2) hold tofacitinib while undergoing treatment with antivirals or antibiotics
  - Hospitalization due to tofacitinib
    - Any patient hospitalized secondary to treatment with tofacitinib as determined by a rheumatology research clinician.
  - Infection with tuberculosis:
    - Patients that develop active mycobacterium tuberculosis. All patients will have undergone screening with a PPD or interferon gamma release assay to rule out TB at the beginning of the study.
  - Treatment failure after week 8

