### **ii Monitoring after tofacitinib cessation**

- If a patient is not a treatment failure as defined by the primary outcome measure at the time of tofacitinib cessation, they will be monitored for disease relapse
- If a patient is a treatment failure at the time of tofacitinib cessation, they will be switched to another steroid sparing agent at the discretion of their treating physician
- Patients who discontinue tofacitinib treatment will remain in the study and be followed to obtain safety data.

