### **G3 Analysis Plan**

All analysis will be descriptive. We expect 40-60% of patients to meet the primary endpoint in each arm similar to adalimumab in the treatment of noninfectious uveitis. This is in contrast to the placebo arm, which had a treatment failure rate of 80% at 24 weeks (12).

Patients will be analyzed by intent to treat when all 5 patients in a treatment arm have either completed 6 months of therapy or discontinued therapy due to study withdrawal or indications for treatment cessation.

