## L Attachments

### L1 Tables

Table 1. Schedule of Laboratory measurements

	Week					
	0	4	8	12	16	24
Clinic visit	X	X	X	X	X	X
CMP & CBC	X	X		X		X
Lipid Panel	X					X
Hepatitis B	X					
Hepatitis C	X					
PPD / IGRA*	X					

\*IGRA: Interferon-gamma release assay a.k.a. T spot for TB

Patients with Hepatitis B & C serologies within the past 5 years will not need repeat labs.

Patients with a PPD / IGRA in the past 12 months will not need repeat labs.

Table 2. Oral steroid (prednisone or equivalent) taper

Week	Prednisone dose (mg/day)
0	60
1	60
2	50
3	40
4	30
5	20
6	15
7	12.5
8	10
9	7.5
10	5
11	4
12	3
13	2
14	1
15	0

Table 3. Prednisone Drop Taper Schedule – patient-specific wherever they start

Dose (# of drops/day) per Week
--------------------------------

12
10
8
6
5
4
3
2
1

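### The only scheduled post-baseline lipid panel is at week 24, so a patient who permanently stops tofacitinib earlier may have the lipid adverse event judged on an off-drug sample

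*Combined protocol and SAP*

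**What the plan says.** - **Event.** Section 5.c gives, as one of its examples of a laboratory adverse event, "Increase of blood lipid and cholesterol levels above baseline and above the normal range". Section 2.e lists raised cholesterol among the known risks, at 5% to 9%.
- **Schedule.** In "Table 1. Schedule of Laboratory measurements" (L1), the lipid panel is marked at weeks 0 and 24 only. CMP and CBC are marked at weeks 0, 4, 12 and 24. E1 ties testing to this table: "Laboratory monitoring (Table 1) will be obtained according to standard of care for drug toxicity monitoring".
- **Stopping the drug.** Section 2.e says: "In the case of a treatment failure based on the primary outcome criteria, tofacitinib will be discontinued". It sets no week limit. Section 2.i, subsection i, lists "Treatment failure after week 8" as an indication for cessation, along with laboratory and clinical reasons.
- **After stopping.** Section 2.i, subsection ii: "Patients who discontinue tofacitinib treatment will remain in the study and be followed to obtain safety data". Patients who have failed are moved to a different agent chosen by the treating physician.
- **Withdrawal.** Under 2.h, follow-up ends when a participant withdraws. The procedures in F4 for later visits, including the Early Exit Visit, name no lipid panel.
- **Expected failures.** G3: "We expect 40-60% of patients to meet the primary endpoint in each arm". C1 defines that endpoint as treatment failure, and G1 caps enrolment at 5.

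**The concern.** The lipid event compares a later value with baseline, so it needs at least one post-baseline result. Only one is scheduled, at the end of the 24 weeks, while the plan expects a sizeable share of patients to fail and takes failing patients off the drug. For someone who stops for good before week 24, that single sample describes a period without tofacitinib, possibly on another agent. No lipid test is linked to the stopping visit, and the plan does not say whether an off-drug value counts towards the event.

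Two errors are possible. A rise that occurred on tofacitinib can go unrecorded, and a rise caused by the replacement agent can be attributed to tofacitinib. In a descriptive pilot of at most 5 patients, each patient's safety record is a large part of the result.

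**Working it through.** The plan gives no power or detection figure to reproduce. Its one relevant figure is G3's expectation.

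**Step 1. Expected failures.** 5 × 0.40 = 2.0 and 5 × 0.60 = 3.0, so 2 to 3 of 5 patients. If G3 meant effectiveness, as B2 does when it describes adalimumab as effective in 40-60%, the complement is again 40-60%.

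**Step 2. Share off drug at the week-24 panel because of failure.** Share s = failure rate × f, where f is the fraction of failures that stop the drug before the week-24 visit. The documents do not say when failures occur, so f is an assumption. Failure can be found at the visits in weeks 4, 8, 12, 16 and 24. A failure first found at week 24 is still on drug when that panel is due. The chance that at least one of 5 patients is affected is 1 − (1 − s)^5.

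| Assumption | f | s | Patients of 5 | Chance of at least one |
|---|---|---|---|---|
| (a) All failures stop the drug before week 24 | 1 | 40-60% | 2.0-3.0 | 0.922-0.990 |
| (b) Failures even over the five visits, 2.e applied (weeks 4, 8, 12, 16 stop) | 4/5 | 32-48% | 1.6-2.4 | 0.855-0.962 |
| (c) Half of failures first found at week 24, the rest stop earlier | 1/2 | 20-30% | 1.0-1.5 | 0.672-0.832 |
| (d) Failures even over the five visits, 2.i applied (only weeks 12 and 16 stop) | 2/5 | 16-24% | 0.8-1.2 | 0.582-0.746 |

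Row (d) takes patients who fail at week 4 or 8 as remaining on drug to week 24. Rows (b) and (d) differ only in which stopping passage is applied, and that choice halves the share. Stops for laboratory or clinical reasons under 2.i would add to every row; the documents give no rate for them.

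**Step 3. Effect on detecting a lipid event, worst case.** Take the risk p from 2.e (5% to 9%) as a fixed per-patient risk. Assume row (a), complete reversal of any rise by the off-drug test, and no unscheduled lipid tests. The chance of seeing at least one event among n patients with an on-drug value is 1 − (1 − p)^n.

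| p | n = 5 | n = 3 | n = 2 |
|---|---|---|---|
| 0.05 | 1 − 0.95^5 = 0.226 | 1 − 0.95^3 = 0.143 | 1 − 0.95^2 = 0.098 |
| 0.09 | 1 − 0.91^5 = 0.376 | 1 − 0.91^3 = 0.246 | 1 − 0.91^2 = 0.172 |

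The chance falls from 23-38% with all 5 patients on drug to 10-25% with 2 to 3 on drug.

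**The case against.** A reader might infer that about half the patients will be tested off drug. The documents do not support that as an expected share. The 40-60% counts failures up to and including week 24, and 2.e and 2.i disagree about failures up to week 8. About half is the ceiling in row (a).

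A reader might also infer that early stoppers have no on-drug lipid value at all. That is too strong. E1 allows extra clinic visits, 5.e has laboratory results reviewed at each visit, and H1 collects laboratory data from the whole medical record, so an unscheduled result may exist, although none is planned. Section 2.i also lets some patients restart after renal recovery, or hold the drug while an infection is treated, and these may be back on tofacitinib by week 24.

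A third inference is that pooled week-24 values would understate the on-treatment rate. That requires the rise to reverse after stopping, and the documents say nothing about reversal or its speed. The detection figures also give every patient the full 5-9% risk regardless of time on drug.

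Finally, little in the plan turns on lipids. The list in 5.c is illustrative. Lipids are not an endpoint, do not trigger cessation, and are not the example given for stopping the trial. The analysis is descriptive, and even complete testing gives only a 23-38% chance of seeing one event.

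All of this limits the size of the point. It does not close the gap: no on-drug lipid value is scheduled for a permanent early stopper, and the plan does not separate on-drug from off-drug results.

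**Conclusion.** The point holds as a minor gap in safety measurement. As scheduled, a patient who permanently stops tofacitinib before week 24 has the lipid event judged on an off-drug sample, and a patient who withdraws may have no post-baseline lipid value.

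Failure-related stops could put up to 2-3 of 5 patients in this position, and fewer (about 16-48%) under the other assumptions examined. Even in the lowest of these, the chance that at least one of 5 patients is affected is 58-75%. The size rests on G3's 40-60%, on the unstated timing of failures, and on which of 2.e and 2.i governs.

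Understatement of on-treatment lipid rises is possible but not established; the fall from 23-38% to 10-25% is a worst case. No alpha or power is affected, because the study claims none.

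**What to change.** - **Table 1:** add a lipid panel to the week-12 draw, where CMP and CBC are already taken, and to the visit at which tofacitinib is stopped or the Early Exit Visit. List the latter in F4 as well.
- **Section 5.c:** add a sentence that lipid values are reported by whether the patient was on or off tofacitinib at sampling.
- **Sections 2.e and 2.i:** reconcile what they say about failure up to week 8, so that the number of patients off drug at week 24 can be interpreted. Which rule applies is for the investigators to decide.

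The cost is one or two extra lipid assays per patient. For anyone still followed at week 12, at least one uses blood already drawn. A stop at week 8 or 16 would need a new sample, since Table 1 has no draw then. The text change is one sentence in 5.c and one line in F4.
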